6.6 Regional crisis between Russia and Ukraine and Related Issues

During the conduct of the FINEARTS-HF study, the conflict between Russia and the Ukraine escalated in February 2022 and, as of finalization of this amendment of the SAP, the regional crisis is ongoing in Ukraine. Every effort will be made to capture the effect of this regional crisis on study conduct.

Crisis-related study disruptions comprise missing visits or procedures, study drug interruptions or permanent discontinuations, AEs related to the regional crisis, and (other) protocol deviations and will be summarized as follows:

- All patients affected by study disruption related to the regional crisis will be listed together with site information and the type of study disruption(s)
- Number of patients affected, number of missed visits, number and type of protocol deviations will be tabulated
- Crisis -related reasons (participant decision, physician decision, or logistical reasons) for premature discontinuation of study epochs (e.g., screen failure, discontinuation of study drug, etc.) and changes in the study treatment (e.g., dose titration, interruption or discontinuation of study drug, etc.) will be included in the relevant summaries
- AEs related to the regional crisis will be included in the relevant summaries; if possible, these will be identified and highlighted in the CSR

See Section 6.5 (COVID-19 and Related Issues) or individual analysis sections for a description of the intercurrent event strategies for the primary and secondary endpoints.

Similarly to the impact of COVID-19, the general approach for these endpoints is still considered valid despite the presence of the regional crisis, considering the following factors:

- Crisis-related study disruptions are expected to be equally likely to occur in either treatment group, therefore not creating bias for the treatment effect
- Information on most adjudicated endpoint events can still be collected even when physical visits cannot take place although incidences or reporting of some adjudicated events might change

Despite this, it is recognized that issues arising from the regional crisis (including but not limited to missing data, data of compromised quality and crisis-triggered intercurrent events) may have a substantial impact on individual data points, patients, sites and/or countries. Therefore, the situation will be monitored on an ongoing basis and a final decision will be made prior to unblinding as to whether specific data-handling rules are required for individual data points, patients, sites and/or countries. This decision will be documented in an SAP amendment or – if that is not possible – a note to file, and all rules will be described and justified in the CSR. Additional summaries and sensitivity analyses may also be required, and these will be reported in the CSR.

For example, due to substantial impact of the regional crisis on a specific site, a decision may be made to censor all study participants from that site at a specific date (e.g. 24-Feb-2022, recognized as the date that the conflict escalated).

Regardless of any decision to implement data-handling rules for data affected by the regional crisis, the following supplemental analyses will be performed to quantify the impact of the regional crisis:

- Primary endpoint (CV death and total HF events)
 - To address the hypothetical scenario in which Ukraine participants did not experience any study disruption due to the regional crisis, two separate analyses will be conducted using the LWYY model described in Section 6.2.1.1 where Ukraine participants are censored at
 - a) Date of first direct or indirect crisis-related study disruption (missed assessment, missed visit, study drug interruption or permanent discontinuation due to the regional crisis)
 - b) 24-Feb-2022, recognized as the date that the conflict escalated (date of the television broadcast “On conducting a special military operation” by Russian president Vladimir Putin)

Additionally, plots and summaries of the mean cumulative function for the primary endpoint (Nelsen-Aalen estimate) will be presented by treatment group.

- To investigate the effect of regional crisis related study disruption on the results of the primary analysis, a time-dependent covariate capturing whether a Ukraine participant is affected by the regional crisis the respective time together with its interaction with treatment group will be included in the LWYY model described in Section 6.2.1.1 Separate models will be used for the two dates described above. Events occurring before and after participants

are affected by the regional crisis will also be summarized by treatment group (separately for FAS and for Ukraine participants in the FAS only)

- Primary efficacy events occurring during interruption of study treatment (due to the regional crisis, or due to other reasons) up to 30 days after any temporary interruption or permanent discontinuation of study treatment will be summarized by treatment group (separately for FAS and for Ukraine participants in the FAS only)
- Total HF events
 - Summaries of HF events occurring before and after participants are affected by the regional crisis, and during interruption of study treatment, will be included as part of the summaries for the primary endpoint described above
- Improvement in NYHA class from Baseline to Month 12
 - Reasons for a participant being classified as “not improved” at Month 12 under the composite strategy will be summarized, including:
 - NYHA measured at Month 12 and not improved from baseline
 - NYHA not measured at Month 12 due to crisis-related reason
 - NYHA not measured at Month 12 due to other reason
- Change from baseline to Month 6, 9 and 12 in TSS from KCCQ
 - No additional summaries or analyses are proposed. This endpoint will be analyzed by a repeated measures mixed model which is valid under the missing at random assumption, and crisis-related study disruptions are expected to be equally likely to occur in either treatment group and therefore not related to study treatment
- Time to first occurrence of renal composite endpoint
 - Events occurring before and after crisis-related study disruption, and during study treatment interruptions due to regional crisis or other reasons, will be summarized by treatment group (separately for FAS and for Ukraine participants in the FAS only)
- Time to ACM
 - Events occurring before and after crisis-related study disruption, and during study treatment interruptions due to regional crisis or other reasons, will be summarized by treatment group (separately for FAS and for Ukraine participants in the FAS only)

7. Document history and changes in the planned statistical analysis

- SAP version 0.4 dated 16 DEC 2019: unsigned draft version for special protocol assessment (SPA) submission
- SAP version 1.0 dated 04 SEP 2020
- SAP version 2.0 dated 24 FEB 2023
- SAP version 3.0 dated 20 JUN 2024

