However, there was a beneficial effect of spironolactone observed in the stratum of patients enrolled on the basis of elevated baseline B-type natriuretic peptide (BNP) or N-terminal pro-B-type natriuretic peptide (NT-proBNP) levels. Furthermore, post hoc analysis revealed marked regional differences in incidence rates, baseline clinical profiles, adverse events, and compliance with study therapies. A  $\approx 4$ -fold lower incidence rate in the composite endpoint was identified between the 1678 patients randomized from Russia and Republic of Georgia compared with the 1767 enrolled from the United States, Canada, Brazil, and Argentina (the Americas). Also, the proportion of patients enrolled on the basis of elevated natriuretic peptide levels versus previous hospitalization for HF was higher in the Americas than in patients from Russia and Georgia. In the Americas region, spironolactone reduced the incidence of the

primary endpoint compared to placebo. In addition, treatment with spironolactone in patients being enrolled from the Americas was associated with more frequent hyperkalemia, elevations in creatinine, reductions in blood pressure, and less hypokalemia ([Pfeffer et al. 2015](#)).

Analysis of the TOPCAT results in the Americas led to the class IIb recommendation added in 2017 to the ACC/AHA guidelines ([Yancy et al. 2017](#)) and gives reason to hope that targeting the MR could result in improved clinical outcome in patients with HFpEF. TOPCAT also prompted further investigation in 2 additional global Phase 3 randomized, open label clinical trials (ClinicalTrials.gov NCT02901184; EudraCT #2017-000697-11) with planned total enrollment of 4500 participants evaluating spironolactone in HFpEF.

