Only adjudicated outcome events will be used for analysis of the primary and secondary efficacy variables (except for sustained decrease in eGFR $\geq 50\%$ relative to baseline over at least 4 weeks and sustained eGFR decline $< 15 \text{ ml/min}/1.73\text{m}^2$ which will be derived from central laboratory measurements and not be adjudicated); Section 6.2.4 specifies how investigator-reported outcomes for these variables will be summarized. Outcome events for exploratory efficacy variables (e.g. non-fatal myocardial infarction, non-fatal stroke, etc.) will not be adjudicated.

The stratified analyses mentioned in this SAP will be conducted in consideration of the randomization stratification factors:

- LVEF: $< 60\%$, $\geq 60\%$
- Pooled region for stratified analyses: randomization will be stratified by country/region, for the analyses individual countries/regions will be combined into pooled regions as follows:
 - Western Europe and Oceania: Australia, Austria, Denmark, Germany, Israel*, Netherlands, New Zealand, United Kingdom
 - Southwestern Europe: Italy, Portugal, Spain
 - Central Europe: Czechia, Hungary, Poland, Slovakia
 - Southeastern Europe: Bulgaria, Greece, Romania, Turkey
 - Northeastern Europe: Finland, Latvia, Lithuania, Russia, Ukraine
 - Asia: China, Hong Kong, India, Japan, Malaysia, South Korea, Taiwan
 - North America: Canada, United States of America
 - Latin America: Argentina, Brazil, Colombia, Mexico

*Although not geographically located in Western Europe or Oceania, Israel has been included in this pooled region.

In case of issues (e.g. model convergence) with using these predefined pooled regions at the final analyses, the pooled regions may be further combined. Any such changes will be described in the CSR.

All participants will be analyzed according to their correct stratification category. In case of a large number of stratification errors ($\geq 5\%$ of all patients in the FAS), the primary analysis will also be repeated based on the stratification category used in the randomization as a sensitivity analysis.

In case a death cannot be clearly adjudicated as CV-related or non-CV related, it will be adjudicated as undetermined death. Undetermined deaths will be handled as non-CV deaths for the analysis, unless otherwise specified. Where applicable, the combined results of non-CV deaths and undetermined death will be displayed along with results for the individual categories.

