6.2.1.1 Primary Efficacy Variable: Primary Analysis

The primary Estimand as defined in Section 2 will be used for the primary analysis. The primary endpoint is the composite of CV death and total (first and recurrent) HF events (HHF or urgent HF visit) in HF patients. The primary analysis of this endpoint will be performed in the FAS using the planned treatment group, in line with the ITT principle.

Participants without an event of the primary composite endpoint at the time of analysis will be censored at the date of their last contact or date of non-CV death.

The number and incidence rate of primary endpoint events and censoring events (i.e. non-CV death) will be summarized per treatment group, both overall and per individual event category. 95% CIs of the incidence rates will be derived based on a Poisson model with robust variance estimator.

The primary analysis of the primary composite endpoint will be based on a stratified Andersen-Gill model (Andersen, 1982) including treatment group as fixed effect and including pooled region for stratified analyses and baseline LVEF ($<60\%$, $\geq 60\%$) as stratification factors. Robust standard errors (sandwich estimator) will be used to account for correlations of event times within a participant. As shown by Lin et al. 2000, the Andersen-Gill model with robust standard errors can be interpreted as a proportional rates model. After the authors of the paper, the model is also referred to as Lin, Wei, Yang and Ying (LWYY) model. Let θ be the RR for the finerenone versus placebo group. In order to evaluate whether finerenone is superior to placebo in reducing the rate of the composite event of CV death and total HF events the following null hypothesis will be tested using the model above (see Section 4.7 for details regarding the nominal significance level):

$$H_0: \theta = 1 \text{ versus } H_1: \theta \neq 1,$$

where $\theta < 1$ represents a treatment benefit of finerenone over placebo.

A point estimate of the RR together with a 95% CI will be presented alongside the point estimate and hazard ratio for the censoring event of non-CV death, calculated using a stratified Cox proportional hazards model.

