The primary analysis method has been investigated with extensive simulation studies and it has been confirmed that it keeps the alpha level and has good operating characteristics across a range of plausible scenarios. A small adjustment will be made to the nominal significance level and the critical value at the final analysis to take into account the interim analysis (see Section 4.7 for details). No adjustment to the sample size calculation is done for this.

The SAS code below illustrates the program for the Anderson-Gill model:

```
PROC PHREG DATA=primary COVS (aggregate);  
  MODEL (time_start, time_rec)*status(0)=treat/ties=efron rl;  
  ID patid;
```

```
STRATA {stratum};  
RUN;
```

primary is the input dataset, time_start is the previous event stop time and time_rec is the current event stop time, the censoring variable status (0 for censored and 1 for event) should take the value 1 if the last event is a CV death and 0 if it is censored for a non-CV death or at the end of study for the given patient; patid is the participant ID and treat is the treatment group identifier.

If a participant experiences an HF event and subsequently dies for a cardiovascular reason, this will be considered as two separate events for the primary analysis unless the participant dies on the same calendar day as the HF event (both events would still be considered for the analyses of the separate components). If a participant is hospitalized for HF shortly after an urgent HF visit, this will be considered as two separate events for the primary analysis unless they occur on the same calendar day.

Additionally, plots and summaries of the mean cumulative function for the primary endpoint (Nelsen-Aalen estimate) will be presented by treatment group.

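### In the two supplemental crisis-covariate models of SAP 6.6, the crisis terms mix change within Ukraine with any pre-existing difference between Ukraine and other participants

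*SAP*

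**What the plan says.** SAP 6.6 plans two covariate models for the primary endpoint, with the stated aim "To investigate the effect of regional crisis related study disruption on the results of the primary analysis". Each takes the LWYY model of SAP 6.2.1.1 and adds "a time-dependent covariate capturing whether a Ukraine participant is affected by the regional crisis the respective time together with its interaction with treatment group". One model uses date (a), "Date of first direct or indirect crisis-related study disruption"; the other uses date (b), 24-Feb-2022, for all Ukraine participants.

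The base model has treatment as its only fixed effect and is stratified, "including pooled region for stratified analyses and baseline LVEF". The illustrative code agrees: "MODEL (time_start, time_rec)*status(0)=treat/ties=efron rl". Randomization is stratified by country/region, but SAP 4.1 states that "for the analyses individual countries/regions will be combined into pooled regions as follows", and one of those pools is "Northeastern Europe: Finland, Latvia, Lithuania, Russia, Ukraine". No Ukraine term and no Ukraine-by-treatment term appears.

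The section also plans two analyses that censor Ukraine participants at these dates. In addition it tabulates events before and after by treatment group, once for the FAS and once for Ukraine participants alone.

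**The concern.** A covariate that can equal 1 in only one country, in a model without a term for that country, partly acts as a country indicator. If Ukraine's event rate differed from that of Finland, Latvia, Lithuania and Russia before the crisis, part of that difference appears in the crisis coefficient. If finerenone's effect in Ukraine differed from its effect in the rest of the trial, part of that appears in the crisis-by-treatment interaction. The COVID-19 covariate in SAP 6.5 is not confined in this way, because it can switch on in any country.

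The two crisis terms are what this model adds to the censoring analyses. A spurious interaction could be read as disruption having weakened or strengthened the drug effect. A masked one could be read as reassurance.

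**Working it through.** **1. Structure.** Let `s` be the pooled-region by LVEF stratum, `C(t)` the crisis covariate and `U` a Ukraine indicator. The planned rate is

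`λ0s(t) · exp{β·treat + γ·C(t) + δ·treat·C(t)}`, with `C(t) = 0` for everyone outside Ukraine.

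If the truth also contains `α·U + η·U·treat`, the omitted terms load on γ and δ.
- The reference for γ is time in the same stratum, at the same follow-up time, with `C = 0`. That is the other four countries plus Ukraine time that is pre-crisis or undisrupted.
- The reference for δ is all `C = 0` time in the trial, because β is common to all strata. Stratification gives no protection there.

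**2. Ukraine time in the reference group, date (b).** The trial started on 14-Sep-2020 (SAP 6.5), and 24-Feb-2022 is about 17.4 months later. Assume that Ukraine entry was uniform over those months, and take the planned 42-month duration (Protocol 9.2).
- Mean pre-crisis follow-up: 17.4/2 = 8.7 months.
- Mean total potential follow-up: 42 − 8.7 = 33.3 months.
- Pre-crisis share: 8.7/33.3 = 26%.

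No Ukraine participant has pre-crisis time beyond month 17.4 after randomization. In later risk sets the covariate is purely Ukraine against the other four countries.

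**3. Calibration.** The documents give no figure for this model, so the planning model of Protocol 9.2 was simulated first. Inputs: 5500 participants, 0.0182 HF events and 0.005125 CV deaths per month, 0.0016 non-CV deaths per month, frailty variance 5.0, effects 0.75 and 0.80, and 5% annual discontinuation. It gave 2375 total events, 1314 first events and 535 CV deaths. The documents state about 2375, 1310 and 535.

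**4. Pure confounding, no frailty and no true crisis effect.** Each scenario had 600,000 simulated participants, with strata by pooled region only. Assumptions not in the documents: Northeastern Europe is 20% of participants; Ukraine is 30% or 60% of that stratum (6% or 12% of the trial); for date (a), 60% of Ukraine participants are disrupted, with a mean delay of 3 months. The rate ratio elsewhere is 0.81. The correct answer in every cell is 1.

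| Pre-existing feature of Ukraine | Term | Date (b) | Date (a) |
|---|---|---|---|
| None | Crisis ratio | 1.01 | 1.00-1.02 |
| Event rate halved | Crisis ratio | 0.50-0.55 | 0.55-0.65 |
| Event rate doubled | Crisis ratio | 1.69-1.90 | 1.37-1.70 |
| Rate ratio 1.0 instead of 0.81 | Interaction ratio | 1.20-1.23 | 1.18-1.28 |

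Share of the rate difference that reaches the crisis term, on the log scale:
- Date (b): from ln 1.691/ln 2 = 76% to ln 0.503/ln 0.5 = 99%.
- Date (a): from ln 1.365/ln 2 = 45% to ln 0.545/ln 0.5 = 88%.

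The true country contrast for the treatment effect is 1/0.81 = 1.235, so nearly all of it reaches the interaction. The treatment coefficient stayed at 0.81-0.82.

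**5. Under the frailty planning model, no true crisis effect.** There were 200 runs per scenario, again with assumed country shares. Significance means a nominal two-sided 5% test.

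| Scenario | Date | Ratio | Significant |
|---|---|---|---|
| Rate halved / doubled | (b) | 0.59-0.63 / 1.38-1.46 | 40-57% |
| Rate halved / doubled | (a) | 0.63-0.69 / 1.19-1.43 | 16-27% |
| No drug effect in Ukraine throughout | interaction | about 1.2-1.3 | 9-11% |

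The Monte Carlo standard error is √(0.5·0.5/200) = 3.5 points near 50% and √(0.1·0.9/200) = 2.1 points near 10%. Large-sample runs with frailty and the step 4 shares gave 0.60-0.63 and 1.36-1.51 for (b), and 0.70-0.72 and 1.20-1.37 for (a).

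For comparison, 300 runs of 6000 participants had Ukraine at 8% of the trial and no different from its stratum. The planned model then rejected the crisis term in 7.0% of runs and the interaction in 7.7%.

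**6. With `ukraine` and `ukraine*treat` added.** Without frailty, the crisis ratio was 0.95-1.05 and the interaction ratio 0.97-1.07 over both dates. With frailty, rejection fell to 4-10% in the step 5 runs and the crisis ratio was about 0.86-1.07. The large-sample frailty runs ranged over 0.84-1.13. A residual in this direction is expected: CV death removes high-risk participants faster where rates are higher, and for date (b) pre-crisis Ukraine time is early follow-up.

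**The case against.** The strongest reply is that the stated aim concerns the primary result, which is the treatment rate ratio, and that the model estimates this soundly in unaffected time. The SAP sets no test or threshold on the crisis terms, so the significance rates above describe how a reader might use them, not a planned decision. This stands, and it confines the problem to interpretation. It does not remove it, because the section introduces these analyses as quantifying the crisis impact and the two terms will be read that way.

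The Ukraine-only before/after tables give part of the missing view. They are descriptive and do not correct the coefficients.

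The sizes come from inputs that the documents do not contain: country shares, a two-fold rate difference, and no drug effect in Ukraine. That also stands.

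Three stronger readings are tempting, and the documents do not support them.
- A reader might infer that the crisis terms contain no before/after information. Pre-crisis Ukraine time is in the reference group, and for date (a) so are Ukraine participants who are not yet or never disrupted.
- A reader might take the Protocol's account of an earlier spironolactone trial, where "post hoc analysis revealed marked regional differences in incidence rates, baseline clinical profiles, adverse events, and compliance with study therapies", as evidence that Ukraine differs from its stratum. That contrast is Russia and Georgia against the Americas. Here Russia shares Ukraine's stratum and the Americas lie in other strata. It shows only that equal rates and effects across countries should not be assumed, which bears mainly on the unstratified interaction.
- A reader might expect the interaction to be falsely significant often. It reached about 10%, little above the 7.7% seen with no country difference.

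**Conclusion.** The concern holds for both supplemental covariate models. As specified, the crisis coefficient and its interaction are not clean crisis effects: each combines a within-Ukraine change with whatever already distinguished Ukraine. The mixing is large but not total, and weaker for date (a) than for date (b). It matters most for the event-rate term. For the interaction, the point estimate is displaced but would seldom be significant. If Ukraine resembles the other countries, nothing is wrong with either term. The actual direction and size cannot be known from the documents.

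It would be wrong to infer that the trial's main result is at risk. The treatment coefficient, the primary test and its alpha, and the two censoring analyses do not depend on these terms. The change is worth making, but it is not critical.

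**What to change.** In both SAP 6.6 covariate models, add a fixed Ukraine indicator and its interaction with treatment, so that the terms are `treat`, `ukraine`, `ukraine*treat`, `crisis(t)` and `crisis(t)*treat`. State that the crisis terms are to be read as a before/after contrast within Ukraine. Stratifying by country instead would deal with the event rate but not with the treatment effect, so the Ukraine-by-treatment term would still be needed.

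The cost is two model terms and a sentence in the SAP. The confidence intervals for the crisis terms will be wider, because they then rest on within-Ukraine information. A small bias remains under strong frailty (step 6). The time axis runs from randomization, so a before/after contrast can also pick up calendar trends such as COVID-19. The report should say so beside the estimates.
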